families (58 families per intervention and control) using a random number table. For random allocation, first, PI will prepare the sampling frame that lists interested families. Second, assign a number to each family in the sampling frame. Third, select 116 numbers using a table of random numbers. PI will request any interested community member to point one number in the random number table by closing his/her eyes. Since the selected families total 116, or three digits, we will choose only the first three digits of the number chosen as the first sampled family. Finally, we will choose other numbers moving down the first number column until all 116 families will be selected.

We will assign a random number selected at the first attempt for intervention and the second attempt for control. It means random numbers selected at odd attempts (first, third, seventh,) will be assigned for intervention and at even attempts (second, fourth, sixth...) for control. The sample elements corresponding to the selected random numbers become the sample. Procedures are in place for tracking the participants for intervention and follow-up (e.g., contact address and phone). RAs will visit selected families and brief them about study procedures, informed consent, and procedures to protect human subjects. All adult members of selected families who meet the inclusion criteria and give informed consent will be recruited for the study. We will follow up with all families randomized to either study arm. We will not follow up with participants if they decide to end their participation at a particular time point of our study. But, we will include their already collected data in our analysis. Given our strong community networks and mobilization of community RAs, we anticipate low attrition rates in practice. Ethical approval for our study will be obtained from the Institutional Review Board at UMass Amherst.

Recruitment of focus group discussion participants

PI will collect data on engagement, acceptability, and satisfaction of intervention delivery by conducting focus group discussions (FGD) with selected interested participants who are already enrolled in our study from the intervention group (30) upon intervention completion using a brief guide questionnaire. The participant will be eligible to attend the focus group discussion if they are already enrolled in our intervention group and have attended our mental health promotion program. RAs will inform participants about FGD

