details verbally while implementing our mental health promotion program. We will recruit interested participants on a first-come-first-serve basis until we get enough participants.

Informed consent procedure

PI will prepare an informed consent document including an explanation on study background, rationale, screening criteria, inclusion and exclusion criteria, study setting, sample size, data collection and intervention procedures, study risks and benefits, privacy and confidentiality of personal information, National Institute of Mental Health Data Archive (NDA) data sharing policy, hair samples collection procedure, storage, and testing procedure, participant compensation, study policy, and study contact person details. PI will train community RAs and field supervisors about processes of taking informed consent from participants.

RAs will inform screening and study procedures to each participant using UMass Amherst IRB approved single informed consent form. A copy of the informed consent form will be provided to each participant for their review. If they want, RAs can read informed consent for them. Participants will be given enough time to review informed consent and ask questions if they have any confusion. RAs will make sure that participants understand about study procedure, privacy and confidentiality of private information, and data sharing policy of NDA. They will be reminded that their participation in the study is voluntary and free to leave the study without penalty. Once participants understand about study details, RAs will request them to do their signature or write their initials or fingerprint for those who cannot write their names in the two copies of the informed consent form before collecting their information. One copy of signed informed consent will be provided to each participant. We will not recruit any individuals who are unable to consent for themselves. The signed informed consent documents will be stored securely in the locked cabinet of the PI's office. (Please see the attached informed consent for details)

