10 DATA COLLECTION AND QUALITY ASSURANCE

10.1 Data Collection Forms

10.1.1 Survey Questionnaire: Trained community research assistants will collect information from participants using attached screening and survey questionnaires and instruction sheets to measure blood pressure, body weight, height, and waist circumferences, and hair samples collection. PI will provide two full days of training to RAs on all aspects of the study procedure, including recruitment procedure, informed consent, screening, pre, and post-assessment survey tools using a questionnaire, anthropometric and blood pressure measurement, hair sample collection and storage procedure, logistics materials, and administrative details. Training sessions include document review, role-play, and practice exercises. We plan to recruit the RAs who worked in our pilot studies to conduct surveys, measure anthropometric parameters and blood pressure, and collect hair samples. The quality of their data collection was excellent in our previous baseline and pilot intervention studies. RAs will complete required human subject research training, including the Collaborative Institutional Training Initiative (CITI) and Good Clinical Practice (GCP).

10.1.2 Screening tool: Trained RAs will use the Patient Health Questionnaire (PHQ-9), a screening questionnaire for depression, to screen the study participants and record each screened participant in the screening log.

10.1.3 Survey questionnaire: Trained RAs will use the survey questionnaire, including various validated scales to measure stress, anxiety and depressive symptoms, coping, social support, social networking, family conflict resolution, and family satisfaction to collect information from the participants at baseline, post-intervention, and 3-month post-intervention. These tools have high internal consistency among the Bhutanese population in our pilot studies (Cronbach's alpha range 0.78 – 0.94).³⁹

10.1.4 Body measures: Trained RAs will follow standard procedures mentioned in the “Training Manual for Research Assistant” to measure blood pressure, body weight, height, and waist circumferences of study participants.

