10.1.5 Hair samples collection: Trained RAs will follow standard procedures mentioned in the “Training Manual for Research Assistant” to collect hair samples of study participants for the stress biomarker measurement. Hair samples will be cut from the posterior vertex of the scalp, carefully placed in aluminum foil, and stored at room temperature until delivery to [name] laboratory at the University of Massachusetts Amherst. Each sample will be cut to a length of 3 cm (if available) from the root (scalp) end and then processed into the [name] laboratory. Briefly, cut samples will be washed twice in 1 ml of isopropanol to remove external contaminants, including cortisol deposited on the outside of the hair shaft from sweat and sebum. After drying overnight, samples will be ground to be fine powder using a bead mill. 1.5 ml of methanol will be added to each sample, after which the samples will be subjected to slow rotation for 18-24 hours to extract the cortisol. 1.0 ml of the extract will be transferred to a clean tube, dried down using a vacuum evaporator, and then reconstituted in 0.25 ml of assay buffer. Reconstituted extracts will be spin-filtered to remove any residual particulate matter and then frozen at -20C for later assay. The cortisol content of each sample will be analyzed in duplicate along with standards and quality controls using the Arbor Assays commercial ELISA kit. Finally, the assay readout will be converted to pg cortisol per mg hair weight.

10.1.6 Confidentiality of participants’ information and record: All interviews will be conducted with the utmost privacy and confidentiality. Each interested adult participant in the family will be interviewed individually, in a private place where they feel comfortable, by our trained community RAs who have worked with the PI in previous intervention studies. The RAs will ensure audio and visual privacy at these sites and ensure data confidentiality. The RAs will assure each participant that their information will be kept confidential and not shared with anybody, including family members, in any context. Moreover, community interventionists will present the PMP-I interventions in family settings welcoming the participation of all interested family members, including parents

and young (<18 years) and old children (aged 18 years and above), without revealing individual participant's data and mental health status.

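### The interviewers who collect the self-report primary outcomes after randomization are not kept from the allocation, and they also invite PMP-I participants to focus groups

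*Combined protocol and SAP*

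**What the plan says.** **Who takes the outcomes.** Section 10.1.1: "Trained community research assistants will collect information from participants using attached screening and survey questionnaires". Section 10.1.3: "Trained RAs will use the survey questionnaire, including various validated scales to measure stress, anxiety and depressive symptoms", collecting "information from the participants at baseline, post-intervention, and 3-month post-intervention". Section 10.1.6: "Each interested adult participant in the family will be interviewed individually, in a private place where they feel comfortable, by our trained community RAs"; section 11.3 repeats this.

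**Masking.** Both the synopsis and section 3 list masking as none. No section provides for a masked or independent outcome assessor, or for a sensitivity analysis of response bias.

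**RA contact linked to the programme.** In section 4.3, on focus-group recruitment, "RAs will inform participants about FGD" is followed by "details verbally while implementing our mental health promotion program". Eligibility for these groups is limited to intervention-arm members who have attended the programme. Section 10.2.2 puts community interventionists, field supervisors and research assistants in the same weekly team meetings.

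**Who delivers and monitors PMP-I.** Section 5.1 gives delivery to trained community interventionists. Section 5.2 gives attendance and fidelity monitoring to field supervisors.

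**What the data are for.** Section 9.2 makes γ001, the between-arm difference at endpoint, the key test. It names estimation of the effect size for a full-scale trial as the ultimate goal.

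**The concern.** PSS and HSCL-25 scores are what the participant chooses to tell the interviewer. Section 2.1 describes the population as typically not literate, so the answers are probably spoken to a member of the same community. If that interviewer knows the family is in PMP-I, or has recently invited the participant to give feedback on it, the participant may report less distress out of courtesy, and the interviewer may probe or record differently. The focus-group contact is described for one arm only, so the effect need not cancel between arms.

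A shift of this kind goes straight into γ001. The multilevel model handles clustering and missing visits, but it cannot separate a reporting shift from a treatment effect. The damage would outlast the pilot, because the full trial would be planned on the inflated effect size.

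**Working it through.** **1. RA duties side by side**

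| Question | What the plan gives | Section |
|---|---|---|
| Who interviews for PSS and HSCL-25? | Community RAs, one to one | 10.1.1, 10.1.3, 10.1.6 |
| When? | Baseline, Day 42, Day 132 | 10.1.3, 6.1 |
| Is the arm withheld from them? | Masking none; no rule | 3 |
| Any RA contact tied to one arm? | Yes, focus-group invitations (PMP-I only) | 4.3 |
| Any other route to the arm? | Joint meetings with interventionists | 10.2.2 |
| Do RAs deliver or monitor sessions? | Assigned to other roles | 5.1, 5.2 |

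Section 4.3 places randomization after the baseline survey, so the exposure concerns the Day 42 and Day 132 interviews.

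**2. The plan's own figure**

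Inputs from section 9.1: ES .30 SD, 116 families (58 per arm), within-family correlation .10, α .05 (two-sided assumed, since sidedness is not stated), 2–4 adults per family. The synopsis gives 226 adults, and 226/116 = 1.95 per family.

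SE of the endpoint contrast in SD units = 2 × √((0.10 + 0.90/m)/116). Power = Φ(0.30/SE − 1.96).

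- m = 4: SE 0.106, power 80.9%
- m = 3: SE 0.117, power 72.4%
- m = 1.95: SE 0.139, power 57.7%

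The stated 80% reproduces at four adults per family. The shortfall at smaller families is a separate matter; these SEs are used here only to scale the bias.

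**3. What a reporting shift would do**

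Let b be the between-arm reporting shift favouring PMP-I. The expected estimate is the true effect plus b. The documents give no value, so b is an assumption. With no true effect, the chance of a significant result favouring PMP-I is Φ(b/SE − 1.96), nominally 2.5%.

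| b (SD) | b/.30 | m = 1.95 | m = 3 | m = 4 |
|---|---|---|---|---|
| 0.05 | 17% | 5.5% | 6.2% | 6.8% |
| 0.10 | 33% | 10.7% | 13.4% | 15.5% |
| 0.15 | 50% | 18.9% | 24.7% | 29.4% |
| 0.20 | 67% | 30.0% | 39.9% | 47.2% |

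**4. A narrower mechanism**

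Suppose only the 30 focus-group members (section 4.3) shifted their answers, with an assumed equal split of 226/2 = 113 adults per arm. The arm mean then moves by 30/113 = 0.265 of the individual shift. An individual shift of 0.10 gives 0.027 SD (9% of .30), and 0.20 gives 0.053 SD (18%). The upper part of the table therefore needs bias across the arm, from interviewers who know the allocation, and not from focus-group contact alone.

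**5. No conversion to scale points**

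The SD of 8.5 in section 9.1 comes from a different trial's anxiety and depression measure. It is not shown to be an SD of the PSS or the HSCL-25, so the shift stays in SD units.

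**The case against.** The strongest reply is that the plan openly declares an unmasked design for a feasibility pilot of a behavioural programme, and that participants will know their arm whoever interviews them. This stands in part. It limits what masking interviewers can achieve, but it gives no reason why interviewers must know the arm.

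There are partial safeguards. Interviews are private, confidentiality is assured, and hair cortisol is included partly to offset the limits of self-report. Privacy and confidentiality do not keep the arm from the interviewer. Cortisol is a secondary outcome, and sections 3 and 6.1 schedule it at baseline and the final visit only, so it cannot check the Day 42 answers.

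A reader might infer more than the text supports:

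- **That RAs attend or help deliver PMP-I sessions.** This rests on one loose clause in section 4.3, which may only say when the invitation is made. Delivery and monitoring belong to others (5.1, 5.2), RA training contains no PMP-I content (10.1.1), and the RA safety-reporting duty in 7.3 does not imply attendance.
- **That the RA home visit discloses the arm.** Section 4.3 says "RAs will visit selected families and brief them about study procedures". This covers all selected families, and disclosure of the arm is not mentioned.
- **That 900 versus 300 session minutes measures unequal interviewer contact.** Those minutes are time in the programmes, not described as RA contact.
- **That bias can arise in PMP-I alone.** Control families also have five study sessions and RA interviews. What matters is the difference between arms.

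Nor do the documents say that the same RA invites and interviews a given family. They simply do not prevent it.

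**Conclusion.** The point holds in a limited form. RAs take the self-report primary outcomes after randomization, nothing withholds the arm from them, and they have one programme-linked contact described only for PMP-I. Interviewer-related bias can therefore enter γ001 and the effect size carried forward. The conclusion does not depend on RAs being present at sessions, which the documents do not establish.

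The direction is an inference and the size an assumption. Over 0.05–0.20 SD, the shift would be 17–67% of the .30 design effect, and the chance of a false positive favouring PMP-I would be about 5.5–47% instead of 2.5%. If only focus-group members were affected, the arm-level shift would be about 0.03–0.05 SD for individual shifts of 0.10–0.20 SD. This is worth changing because the remedy is cheap and the effect size is the pilot's main product. It does not invalidate the design.

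**What to change.** In sections 4.3, 10.1.1 and 10.1.3, state that:

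- Day 42 and Day 132 interviews are done by existing RAs who are not given the arm list, have no programme contact with that family, and take no part in focus-group invitations.
- The PI, who already conducts the focus groups, issues the invitations. Moving them to interventionists or field supervisors would bring courtesy and pressure into the acceptability data, because their own work is under evaluation.
- A script asks participants not to mention which programme they attended.
- After each interview the RA records whether the arm became known.

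In section 10.2.2, keep discussion that identifies a family's arm out of the meetings RAs attend. Amend the masking entries in the synopsis and section 3 to match. Leave the safety-reporting duties in 7.3 as they are, and record any unmasking that follows from them.

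The cost is one script line, one form item, some PI time and less flexible scheduling. The plan does not give the number of RAs, so using existing staff assumes there are enough to separate the roles. Masking will be incomplete in a small community, and bias from participants knowing their own arm remains. The unmasking record would also show whether masked assessment is workable in the full trial.

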5 STUDY INTERVENTIONS

5.1 Interventions, Administration, and Duration

Intervention group: Each participant's involvement will be 5-sessions of the PMP-I program of 180 minutes each for a total of 900 minutes. We will request intervention group participants to complete five sessions of PMP-I intervention. Each session is about 180 minutes. Our proposed family-based mental health intervention is a 5-week, culturally tailored stress management, behavioral activation, problem-solving (90 minutes), and mind-body exercises, including yoga and breathing exercises (90 minutes) at a family level delivered by trained community interventionists at their family settings.

Control group: We also plan to implement five talk programs about community support services to control group participants. Each participant's involvement will be 5-sessions of a talk program of 60 minutes each for a total of 300 minutes.

Post-Intervention for Control group: Each participant's involvement will be 2-sessions of mental health intervention of 120 minutes each for a total of 240 minutes.

Training for Community Interventionists: We will train community members to deliver the intervention in family settings. [name] will provide 12 full-day training to the community interventionists in collaboration with PI and [name] [name] following the World Health Organization PM+ training manual. We will provide a PMP-I program manual describing the procedure of delivering each intervention component to community interventionists. They will use the intervention manual to provide PMP-I to community members at family settings under field supervisors and PI's supervision. (Please see attached the PMP-I intervention manual for the details)

Local community members with a high school level of education and no formal training or prior experience with mental health service providers will deliver the PMP-I. First, Drs. [name] and [name] will review with the PI the PMP-I Manual, fidelity checklists, and other training materials. Second, [name] will provide ten full days (80 hours) of intensive classroom training to community interventionists (CI) using the PMP Helpers' Training Guide. Classroom training includes information about stress and depression, the rationale for each of the strategies, necessary helping skills, extensive role-plays, peer observations, and group discussion related to core intervention concepts. Third, [name] will provide an additional two days of training in supervision to the same CIs so that they can play the

dual role of interventionists and supervisors as needed. Supervision involves discussing participants' progress and difficulties experienced when delivering strategies and role-playing on managing problems or practicing skills. Fourth, following classroom training, the PI will provide field training with at least two participants for five sessions. Finally, after overall training, we will conduct a formal evaluation of the interventionists' readiness to implement/supervise the PMP-I intervention such as using the manual, answering questions, and managing time, using a fidelity checklist, practice exercise, and role play, and will provide feedback as necessary.

[name] will provide 4 hours of breathing exercises and 16 hours of yoga practice to CIs and field supervisors using a Yoga Training Guide. Classroom training includes theoretical and practice exercises to guide participants in mind-body exercises for attention to breath, body sensation, emotional awareness, and mental function on different postures of yoga practices such as *Pranayama* (3 poses) and *Asana* (21 poses). Training will include practice assessment at the end to ensure that all staff was adequately trained, using a checklist, practice exercise, and role-plays. (Please find attached the mind-body exercise manual for the details)

Intervention Components

Psychoeducation: A brief educational session on stress management to increase awareness of the health benefits of reducing stress. To address the social isolation of many immigrants' in a new culture, we plan to educate on multi-cultural communication and social networking to promote their cross-cultural interaction.

Behavioral activation (BA): In BA, we plan to propose behavior modification activities with a specific focus on identifying and strengthening positive coping styles for immigrants adapting to a new cultural environment as members of the immigrant community feel relief talking in person and prefer doing culturally appropriate behavior modification activities to other more traditional western psychotherapies.

Problem-solving (PS): In PS, we plan to include practice exercises in identifying and trying at least three best problem-solving measures that would help manage stress, and strengthening coping, communication, and social networking skills.

Mind-Body Exercise (MBE): Yoga and breathing exercises are a mind-body intervention scientifically sound and well known in the community. They are included in our intervention as community members viewed yoga and breathing exercises as a culturally preferred essential part of stress management and are critical contributors to the stress reduction observed in our pilot programs.

Strengthening social support (SS): In SS, we plan to include practice exercises to identify and try at least three best social events that would help make them feel better and happy.

5.2 Adherence Assessment

The PMP trainers training guidelines developed by the World Health Organization provide specific tools for evaluating and monitoring the intervention that we will use to monitor fidelity of intervention delivery. These tools are PMP Quiz, PMP Helper's Supervision Form, PMP Helper Classroom-based Competency Assessment, PMP Helper In-field based Competency Assessment, PMP Trainer/Supervisor Competency Assessment, and Session-by-Session Checklists for PMP Helpers. We have adapted these tools in the context of our program contents. (Please find attached PMP-I program monitoring tools for the details)

Using these standard tools, we will evaluate session-by-session classroom and in-field based competencies of participants, community trainers, and supervisor and provide them feedback as needed using supervision forms, role-plays, group discussion, and training. After each session and program completion, the field supervisor will collect data on engagement, acceptability, and satisfaction via a brief questionnaire and qualitative interviews with community interventionists. The field supervisor will also collect data on adherence to the manual, percent of intervention content administered, proper use of time and materials, and adequate response to participants' questions through field observation of community interventionists' work.

Field supervisors will collect data on eligibility, recruitment and enrollment, intervention session attendance (including reasons for missed sessions), and compliance with data collection procedures, including hair sample collection and anthropometric measurements using a checklist. They will monitor intervention sessions using WHO standard checklists. Items include adherence to the manual, percent of intervention content administered, proper use of time/materials, and adequate response to participants' questions. They will also collect data on engagement, acceptability, and satisfaction via

brief questionnaires and focus group discussions (FGD) with participants and interventionists after each session and upon intervention completion.

The PI will conduct FGD in the Nepali language with interventionists, supervisors, and participants separately to collect information on barriers and facilitators of intervention, perceptions about whether the intervention met participants' needs, and feedback on how effectively the program team worked with participants. Interviews and FGD will be documented verbatim in a written transcript for subsequent analysis. All qualitative data will be analyzed using thematic content analysis.⁵³ Feedback provided by the field staff will be reviewed and coded to identify recurrent themes regarding the intervention's acceptability. All analyses will be conducted in Nepali and translated into English. Fidelity data will be used to assess intervention content and transmission. We will determine retention by obtaining proportions of participants attending all or portion of sessions.

